8.2 Disease Assessment

Assessment of disease response will follow the criteria outlined in the Revised Recommendations of the International Working Group (IWG) for Diagnosis, Standardization of Response Criteria, Treatment Outcomes, and Reporting Standards for Therapeutic Trials in Acute Myeloid Leukemia. (35) Investigators are encouraged to consult the reference for more detailed explanation of response criteria.

CR, CRi/CRp, and PR are defined using the following criteria:

Morphologic CR:

- A CR designation requires that the patient achieve the morphologic leukemia-free state and have an ANC of more than 1,000/uL and platelets of > 100,000/uL.
- A morphologic leukemia-free state requires less than 5% blasts in an aspirate sample with marrow spicules and with a count of at least 200 nucleated cells.
- There should be no blasts with Auer rods.
- Hemoglobin concentration or hematocrit has no bearing on remission status, although the patient must be independent of transfusions.
- There should be no residual evidence of extramedullary leukemia.

Morphologic CRi, CRp:

After chemotherapy, some patients fulfill all of the criteria for CR except for residual neutropenia (<1,000/uL) or thrombocytopenia (<100,000/uL).

PR:

- This designation requires all of the hematologic values for a CR but with a decrease of at least 50% in the percentage of blasts to 5% to 25% in the bone marrow aspirate. Thus, if the pretreatment bone marrow blast percentage was 50% to 100%, the percentage of blasts must decrease to a value between 5% to 25%; if the pretreatment blast percentage was 20% to less than 49%, they must decrease by at least half to a value of more than 5%.
- A repeat bone marrow aspiration after several weeks may be required to distinguish between a PR and increased blasts caused by bone marrow regeneration.
- A value of < 5% blasts may also be considered a PR if Auer rods are present.

Progressive Disease:

Because the IWG criteria for AML do not provide a standardized definition for progressive disease, in this protocol, progressive disease is defined as 1 of the following:

- >50% increase in bone marrow blasts from baseline value.
- >50% increase in circulating blasts from baseline value with absolute blast count $> 1000/\text{mm}^3$
- Development of biopsy-proven extramedullary disease, or new sites of extramedullary leukemia.
- Note: If the initial marrow blast percentage is too high to base progression on a >50% increase in bone marrow blasts, then peripheral blood criteria will be used.

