2.2 Endpoints

2.2.1 Primary Endpoint

Phase I: Maximum tolerated dose (MTD) and recommended Phase II dose (RP2D) for the combination of TAK-659 plus Ixazomib in relapsed or refractory AML

Phase II: Overall response rate (ORR) defined as CR, CRp, CRi, and PR per Revised Recommendations of the International Working Group (IWG) for Diagnosis, Standardization of Response Criteria, Treatment Outcomes, and Reporting Standards for Therapeutic Trials in Acute Myeloid Leukemia.

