2.2.2 Secondary Endpoints

- DOR defined as the time from the date of first documentation of a response to the date of first documented progressive disease
- TTP defined as the time from first dose of study drug until tumor progression as defined by the Revised Recommendations of the International Working Group (IWG) for Diagnosis, Standardization of Response Criteria, Treatment Outcomes, and Reporting Standards for Therapeutic Trials in Acute Myeloid Leukemia
- Mortality rate at 3 and 6 months
- OS defined as the time from the date of study entry to death
- ORR, DOR, TTP, mortality rate at 3 and 6 months, and OS in Flt3mutant vs. WT populations

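### DOR ends only at progressive disease measured against the pre-treatment value, with relapse and loss of PR not listed, so some responders' end of response can be dated late or missed

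*Combined protocol and SAP*

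**What the plan says.** Section 2.2.2 gives "DOR defined as the time from the date of first documentation of a response to the date of first documented progressive disease". Section 13.7.2 repeats that single end event. DOR starts at any response counted in the primary endpoint: "Overall response rate (ORR) defined as CR, CRp, CRi, and PR per Revised Recommendations" (Section 2.2.1).

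Sections 8.2 and 10 define progressive disease as one of three things:

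- marrow: ">50% increase in bone marrow blasts from baseline value";
- blood: circulating blasts more than 50% above baseline and also above 1000/mm³;
- new extramedullary disease.

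A note adds that the blood criteria apply if the initial marrow percentage is too high for the marrow rule. Baseline is the pre-treatment value: that note speaks of the initial marrow, and Section 8.3 calls the screening marrow the baseline procedure.

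Relapse appears only in text about sampling. Footnote 13 of the phase 2 calendar equates relapse with PD in a parenthesis. The calendar row marks the same sample as taken at PD, and Section 9.1 lists it under progression. Section 8.3 asks for a marrow when a phase II responder shows clinical signs of relapse. None of these gives a blast level.

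For TTP, Section 2.2.2 runs from first dose "until tumor progression as defined by the Revised Recommendations of the International Working Group". Section 8.2 introduces its own list with "Because the IWG criteria for AML do not provide a standardized definition for progressive disease".

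**The concern.** DOR should stop when the response is over. Here it stops only when the disease is clearly worse than before treatment, which is a different and later state. A patient who has lost CR or PR, and whose marrow is back where it started, meets no marrow criterion on the list.

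For responders the error has one direction: apparent response is lengthened. DOR and TTP are descriptive secondary endpoints, but Section 13.2 says that both will also be considered in the decision to expand the study. Section 13.1 summarises time-to-event data by Kaplan-Meier percentiles, and with few responders a few late dates can move a DOR percentile.

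**Working it through.** The plan states no DOR figure to reproduce, so the check is arithmetic on its own thresholds.

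**Marrow limits.** Let B be the pre-treatment marrow blast percentage.

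- Marrow progression: above 1.5 × B (Sections 8.2 and 10).
- Loss of CR: 5% or more, because CR requires fewer than 5% blasts (Section 8.2).
- PR ceiling: B/2 for B from 20% to under 49% ("they must decrease by at least half to a value of more than 5" percent); 25% for B of 50% or more.

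| B | CR lost at | PR lost above | Marrow progression above | Progression limit ÷ PR ceiling |
|---|---|---|---|---|
| 20% | 5% | 10% | 30% | 3.0 |
| 40% | 5% | 20% | 60% | 3.0 |
| 50% | 5% | 25% | 75% | 3.0 |
| 60% | 5% | 25% | 90% | 3.6 |
| 66.7% | 5% | 25% | 100% | 4.0 |

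For B from 20% to under 49% the ratio is 1.5B ÷ 0.5B = 3.0. From 50% it is 1.5B ÷ 25. The marrow limit reaches 100% at B = 100 ÷ 1.5 = 66.7%; from there marrow progression is unreachable and only blood or extramedullary disease can end DOR. At every baseline, a return to 1.0 × B is below 1.5 × B.

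**Which limit is the comparator.** Because ORR counts PR, the PR ceiling is the nearest comparator for the end of overall response; 5% marks loss of CR. For a CRp or CRi patient whose counts have not recovered, 5% also marks loss of any response, since PR is no fallback: "This designation requires all of the hematologic values for a CR".

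**Reading baseline as the nadir.** This does not rescue the rule. A 2% nadir gives 1.5 × 2 = 3%, which is still within the CR range.

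**How many responders.** Design rates and stage rules are from Section 13.2. They are applied to whatever response is counted, with no allowance for replacements. FLT3-WT: 9 patients, continue with 2 or more responses, then 7 more; rates 15% and 40%. FLT3-mutant: 8 patients, continue with 3 or more, then 12 more; rates 30% and 55%.

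Given full accrual, expected responders = E(stage-1 responses, given continuation) + n₂ × p:

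- Null: WT 2.45 + 7 × 0.15 = 3.50; mutant 3.59 + 12 × 0.30 = 7.19; total 10.7.
- Alternative: WT 3.81 + 7 × 0.40 = 6.61; mutant 4.65 + 12 × 0.55 = 11.25; total 17.9.

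Allowing for stage-1 stopping, expected responders = n₁ × p + P(continue) × n₂ × p:

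- Null: WT 1.35 + 0.401 × 1.05 = 1.77; mutant 2.40 + 0.448 × 3.60 = 4.01; total 5.8.
- Alternative: WT 3.60 + 0.929 × 2.80 = 6.20; mutant 4.40 + 0.912 × 6.60 = 10.42; total 16.6.

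Under the null, both cohorts reach full accrual with probability 0.401 × 0.448 = 0.18.

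**TTP.** For a non-responder, comparison with baseline is an ordinary progression rule. The problem concerns responders only. Separately, Section 2.2.2 takes progression from a source that Section 8.2 says has no standardized definition of it.

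**The case against.** The best defence is that the authors plainly think of relapse as PD. Footnote 13, the calendar row and Section 9.1 all treat a responder's relapse sample as a progression sample, and Section 8.3 requires a marrow at clinical relapse. If investigators record relapse as PD, DOR is dated about right. This stands as evidence of intent, and it rules out the inference that the plan means to count relapsed patients as still responding. But the passages concern sampling, give no threshold and do not amend the list, so two sites could date the same relapse differently.

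The blood and extramedullary criteria will also catch some relapses, for example a patient with few circulating blasts at baseline who later exceeds 1000/mm³. So a reader should not infer that every responder's DOR is late or missed. The exposure is marrow-only relapse, loss of PR, and blood relapse below the criterion.

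Section 8.2 refers investigators to the International Working Group (IWG) paper for more detail on response, and that paper was not available for this review. It may contain a relapse criterion. Even so, DOR is tied to progressive disease, which Section 8.2 makes the protocol's own definition.

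Finally, the endpoints are secondary and have no decision threshold. That is correct and limits the weight of the point.

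**Conclusion.** The DOR rule is wrong as written and should be changed. Applied literally, it keeps a responder with marrow-only relapse or loss of PR in response until blasts exceed 1.5 times the pre-treatment value, which is 3 to 4 times the PR ceiling where it can be reached at all. TTP for responders shares the fault. This assumes that baseline means the pre-treatment marrow, and that the blood and extramedullary criteria are not met and the investigator does not record relapse as PD.

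The effect is confined to descriptive secondary endpoints among roughly 11 to 18 responders at full accrual, or 6 to 17 allowing for stage-1 stopping. Three stronger readings are not supported:

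- ORR, the Simon rules, OS and the 3- and 6-month mortality rates do not use this definition.
- No delay in days can be given, because the documents contain no blast growth rate.
- Deaths in response cannot be said to lengthen DOR, because no censoring rule is stated. Death, transplant and new therapy need their own rules and are not part of this error.

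**What to change.** For endpoint dating only, leaving the definition in Sections 8.2 and 10 and all treatment rules unchanged, end DOR at the first of:

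1. relapse after CR, CRp or CRi: marrow blasts of 5% or more not attributed to regeneration, or reappearance of leukemic blasts in blood;
2. loss of PR: marrow blasts above the protocol's PR range for that patient's baseline;
3. progressive disease per Sections 8.2 and 10.

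State that for CR patients this dates loss of CR. A CR patient at 8% has then ended while a PR patient at 8% has not, so time to blasts above the PR range could be reported as well. Define TTP by Sections 8.2 and 10 plus the same relapse rule, not by IWG. Reconcile the phase 2 calendar row, footnote 13, Section 8.3 and Section 9.1 with the list. Extend off-treatment collection of progression from local data, now stated for CR patients (Duration of Study under Section 5.1, calendar footnote 3, Section 8.7), to all responders.

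The cost is endpoint wording and modest extra data collection; Section 8.3 already calls for the relapse marrow. Reported DOR will be shorter, and its event can differ from treatment-defining PD. There is also counting noise near the limits. At the CR minimum of 200 cells, an observed 5% has an exact 95% CI of 2.4% to 9.0%, and 20% has 14.7% to 26.2%. A true 3% marrow reads 5% or more with probability 0.08; a true 15% reads above 20% with probability 0.02. Section 8.2 already has a tool for values near a limit: "A repeat bone marrow aspiration after several weeks may be required to distinguish between a PR and increased blasts caused by bone marrow regeneration". Later marrows are done as clinically indicated, so dates stay approximate under either rule.

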12. Bone marrow biopsy and aspirate for disease burden (blast counts), cytogenetics, and cellular composition by flow cytometry will be done at screening. In addition, BM aspirates and/or biopsies will be done to assess disease response at Cycle 1 Day 15 and Cycle 3 Day 22, so that the results are available before Day 1 of the next cycle. In the post-Cycle 3 assessment, aspirate and biopsy are suggested on day 22 (or within 3 days prior to C4D1), simultaneous with the plan to continue onto C4 D1, to serve as record establishing the optimal response/composite CR. Such planning should be guided by the trend of blast reduction observed during Cycles 1, 2. After Cycle 3 assessment, BM biopsy and/or aspirate assessment will be performed as clinically indicated based on changes in peripheral blood counts, or when it is needed to establish either CR or disease progression. NOTE: a BM biopsy is required at screening and post-Cycle 3 D22. Residual and/or additional bone marrow samples will be requested for biomarker analysis. In cases when insufficient BM aspirate is collected, peripheral blood will be submitted per the instructions in the CLM.
13. BM timing (D4 vs D8) will be determined from results in the Phase I patients. At the time of relapse (PD) of any patient who had initially responded to TAK-659, bone marrow aspirate and/or biopsy materials will be collected for biomarker study.
14. Blood for PK plasma samples will be collected at : C1D1 (pre-dose, 2-4 hr post-dose), C1D15 (pre-dose, 2-4 hr post-dose), Cycle 2, 3, 4 Day 15 (pre-dose, post-dose anytime during clinic visit). Instruct patient withhold study drug(s) for that day. The timing of the visit should be planned so that the pre-dose PK draw occurs near the same time as the previous day's dosing. When a blood sample coincides with the timing of an ECG,

the ECG will be completed first. Refer to the CLM for detailed instructions on collection, processing, storing, and shipping of PK samples.

15. Whole blood for banking is to be collected at predose C1D1. Serum and plasma for banking are to be collected at pre-dose C1D1 and at the 30-Day Safety Follow up visit. See CLM for collection, processing, labeling and shipping instructions.

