10. CRITERIA FOR DISEASE EVALUATION

Assessment of disease response will follow the criteria outlined in the Revised Recommendations of the International Working Group (IWG) for Diagnosis, Standardization of Response Criteria, Treatment Outcomes, and Reporting Standards for Therapeutic Trials in Acute Myeloid Leukemia. (34) Investigators are encouraged to consult the reference for more detailed explanation of response criteria.

CR, CRi/CRp, and PR are defined using the following criteria:

Morphologic CR: A CR designation requires that the patient achieve the morphologic leukemia-free state and have an ANC of more than 1,000/uL and platelets of \geq 100,000/uL. A morphologic leukemia-free state requires less than 5% blasts in an aspirate sample with marrow spicules and with a count of at least 200 nucleated cells. There should be no blasts with Auer rods. Hemoglobin concentration or hematocrit has no bearing on remission status, although the patient must be independent of transfusions. There should be no residual evidence of extramedullary leukemia.

Morphologic CRi, CRp: After chemotherapy, some patients fulfill all of the criteria for CR except for residual neutropenia ($<1,000/\mu\text{L}$) or thrombocytopenia ($<100,000/\mu\text{L}$).

PR: This designation requires all of the hematologic values for a CR but with a decrease of at least 50% in the percentage of blasts to 5% to 25% in the bone marrow aspirate. Thus, if the pretreatment bone marrow blast percentage was 50% to 100%, the percentage of blasts must decrease to a value between 5% to 25%; if the pretreatment blast percentage was 20% to less than 49%, they must decrease by at least half to a value of more than 5%. A repeat bone marrow aspiration after several weeks may be required to distinguish between a PR and increased blasts caused by bone marrow regeneration. A value of $\leq 5\%$ blasts may also be considered a PR if Auer rods are present.

Progressive Disease

Because the IWG criteria for AML do not provide a standardized definition for progressive disease,⁽¹²⁾ in this protocol, progressive disease is defined as 1 of the following:

- $>50\%$ increase in bone marrow blasts from baseline value.
- $>50\%$ increase in circulating blasts from baseline value with absolute blast count $> 1000/\text{mm}^3$
- Development of biopsy-proven extramedullary disease, or new sites of extramedullary leukemia.

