13.7 Data Analysis Plan

13.7.1 Primary Objective

Phase I portion: There is no primary efficacy endpoint for the dose escalation portion of the study. Toxicity data will be summarized and tabulated for all and for each dose level.

Phase II portion: The phase II is not intended to demonstrate differences in treatment outcomes among disease groups, although potentially informative data will be subjected to exploratory analysis. The primary endpoint is ORR. ORR is defined as the rate of CRs and PRs in the response-evaluable population. It will be estimated with 95% exact binomial confidence intervals (CIs), while considering the adaptive nature of Simon's two-stage design.

13.7.2 Secondary Objectives:

There is no secondary efficacy endpoint for the Phase I portion of the study.

Phase II study: the secondary efficacy endpoints for are ORR in FLT-3 mutant and FLT-3 WT populations, DOR, mortality rate at 3 and 6 months, and OS (by FLT-3 mutant cohort, FLT-3 WT cohort, and combined cohort). DOR is defined as the time from the date of first documentation of a response to the date of first documented progressive disease (TTP). OS is defined as the time from the date of study entry to death. ORR will be estimated with 95% exact binomial confidence intervals (Cis). Time-to-event data will be analyzed by the Kaplan-Meier method. OS at 3 and 6 months and by FLT-3 mutant cohort, FLT-3 WT cohort, and combined cohort) will be estimated using the Kaplan-Meier along with 95% CIs.

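### Duration of response has no event when a responder relapses to pre-treatment blast levels, because blast progression is measured only against baseline

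*Combined protocol and SAP*

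**What the plan says.** Section 2.2.2 gives "DOR defined as the time from the date of first documentation of a response to the date of first documented progressive disease". Section 13.7.2 closes the interval at the same event and attaches the label TTP to it. Neither section names relapse as an event.

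Section 8.2 explains that the "IWG criteria for AML do not provide a standardized definition for progressive disease" and therefore supplies its own list, which Section 10 repeats. Any one of three findings is progressive disease:

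- marrow: ">50% increase in bone marrow blasts from baseline value";
- blood: circulating blasts up by more than 50% from baseline, with an absolute count above 1000/mm3;
- extramedullary disease that is new or biopsy-proven.

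A note covers high starting values: "If the initial marrow blast percentage is too high to base progression on a >50% increase in bone marrow blasts", the blood criteria apply instead. The note speaks of the initial percentage, and Section 8.3 treats the screening marrow as the baseline one, so baseline means pre-treatment.

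Relapse is mentioned elsewhere without a threshold. Footnote 13 of the Phase II calendar (Section 8) asks for marrow material "At the time of relapse (PD) of any patient who had initially responded to TAK-659". Section 8.3 asks for a marrow when a responder shows clinical signs of relapse.

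For TTP, Section 2.2.2 runs the clock "until tumor progression as defined by the Revised Recommendations of the International Working Group (IWG"), the source that Section 8.2 says has no standardized definition.

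**The concern.** A pre-treatment reference suits a patient who has never responded. It does not suit a responder, whose blasts have already fallen well below baseline. Loss of remission is then invisible to the blast criteria until the leukemia exceeds its original burden by half.

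DOR is a secondary endpoint. Section 13.1 summarizes time-to-event data by Kaplan-Meier quartiles, and Section 13.2 says that DOR will be weighed when deciding whether to expand the study. Responders will be few. At the minimum counts for a positive result (5 of 16 in the wild-type cohort, 8 of 20 in the mutant cohort), one misdated relapse is 1/5 = 20% or 1/8 = 12.5% of that cohort's DOR data. A reader who applies the Section 8.2 list and one who follows the calendar footnote would also give the same patient different durations.

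**Working it through.** The plan states no DOR or TTP assumption, so there is no figure to reproduce. The check applies the Section 8.2 rule to example patients. The patient values are illustrative; the rules and the 5% remission limit come from Section 8.2.

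**Marrow rule.** Progression requires blasts above 1.5 × b, where b is the pre-treatment percentage.

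| Pre-treatment b | Level to exceed (1.5 × b) |
|---|---|
| 20% | 30% |
| 40% | 60% |
| 60% | 90% |
| 66.7% | 100% |
| 80% | 120% (impossible) |

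The limit of reach is b = 100/1.5, about 66.7%. A return to b is a rise of (b − b)/b = 0% at every baseline.

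**Example patients.**

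- CR, 40% → 3% → 40%. Against baseline: (40 − 40)/40 = 0%, not progression. Against the remission value: (40 − 3)/3 = +1233%.
- PR, 40% → 15% → 40%. Against baseline: 0%, not progression. Against the lowest value: (40 − 15)/15 = +167%.
- CR, 80% → 3% → 80%. Against baseline: 0%, and no marrow value could qualify.

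A patient with a 40% baseline can therefore move from under 5% up to 60% with no marrow event.

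**Blood rule.** Progression requires a count above both 1.5 × c and 1000/mm3, where c is the pre-treatment count. For c = 5,000/mm3 the count must exceed 7,500; a return to 5,000 is not progression. For c = 2,000/mm3 a return to 2,000 is not progression. The two limits cross at c = 1000/1.5, about 667/mm3.

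**What is still caught.** Relapse counts if it is extramedullary, or if c was about 667/mm3 or less and the relapse count exceeds 1000/mm3. It also counts later if marrow or blood overshoots 1.5 times its own baseline. A relapse that restores the pre-treatment marrow and blood levels meets none of these.

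**Direction.** For a CR patient with any b of 20% or more, the marrow event level (at least 30%) lies above the 5% at which remission is lost. The literal marrow event therefore cannot come before loss of remission. It comes at the same look, later or never, so the error runs toward longer DOR.

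**The case against.** The intent is visible. The calendar footnote treats relapse as progression, Section 8.3 already calls for a marrow at relapse, and Section 8.2 adopts the IWG response criteria and sends investigators to them. Whether that paper defines relapse cannot be checked here. This stands as evidence of intent, but the footnote is a sampling instruction with no blast level, and the explicit list in Section 8.2 does not include relapse.

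The plan also foresaw high marrow baselines and moves those patients to the blood criteria. A reader might infer that such patients can never progress; that is not so. The fallback works when few blasts circulated before treatment, or when the count overshoots. It does not help when blood blasts return to their own baseline.

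Three further inferences go too far:

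- **Median DOR is inflated by a known amount.** That would need relapse times, baseline blast distributions, regrowth rates, marrow timing and exits to transplant or other therapy. The documents give none of these in usable form, and later marrows are done only as clinically indicated.
- **Patients must be treated through relapse.** Section 5.3.1 makes marrow progression a cue to stop, and Section 6.4 lets the physician change therapy at any time.
- **The primary analysis is affected.** ORR and the two-stage rules use achieved response, not its duration.

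No DOR threshold drives a decision, so the stakes are limited.

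**Conclusion.** The concern holds for DOR. As written, a responder who relapses to pre-treatment marrow and blood levels has no DOR event, and the marrow criterion is out of reach from a baseline of about 66.7%. This is a stated rule that gives the wrong duration when followed, and it disagrees with the plan's own shorthand for relapse. The direction is upward; the amount cannot be computed from the documents. TTP has a related fault, since Section 2.2.2 sends it to a source that Section 8.2 says has no standardized definition.

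The conclusion rests on reading baseline as pre-treatment, which Sections 8.2 and 8.3 support, and on there being no operative relapse threshold in the supplied text. It should be corrected before DOR is analyzed.

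**What to change.** 1. In Sections 8.2 and 10, add a rule for responders. After CR, CRi or CRp, relapse is any of: marrow blasts of 5% or more not attributable to regeneration, reappearance of leukemic blasts in blood, or new extramedullary disease.
2. After PR, progression is a rise of more than 50% over the lowest on-study marrow value, above an absolute floor and not attributable to regeneration. Without a floor, a PR at 6% would progress just above 1.5 × 6 = 9%. One candidate floor is 25%, the plan's own PR ceiling; that patient would then need more than 25%. A 25% floor would still miss a return to a pre-treatment level of 20–25%, so the sponsor may prefer a lower value.
3. Keep the baseline rule for patients who have not responded.
4. In Sections 2.2.2 and 13.7.2, end DOR at the first relapse or progression under Section 8.2. In Section 2.2.2, point TTP to Section 8.2 instead of the IWG document.

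The cost is mainly wording. A marrow at relapse is already called for in Section 8.3; the likely addition is a repeat marrow in equivocal cases, which Section 8.2 already foresees for PR. Reported DOR will be shorter than under the literal rule. The thresholds are proposals, and the sponsor may set others.
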